4. PATIENT REGISTRATION AND ENROLLMENT PLAN

4.1 Registration Procedure

Prior to protocol enrollment and initiation of treatment, subjects must sign and date an IRB approved consent form. A centralized, 3-part registration procedure will be used. After eligibility screening and confirmation that a patient is eligible, patients who are selected to participate will be registered centrally at the SKCCC Johns Hopkins Lead Center, at the participating institution, and if applicable, in the online centralized PCCTC database. A record of patients who fail to meet entry criteria (ie, screen failures) will be maintained. The patient must give informed consent before beginning any study-specific procedures. Patient registration must be completed by the lead coordinating center before treatment is initiated. A complete, signed study consent and HIPAA consent are required for registration.

4.1.1 *Registration at SKCCC, Johns Hopkins University*

Confirm eligibility as defined in **Section 3. Patient Selection.**

4.1.1.1 Obtain informed consent, by following procedures:

The investigator (or his/her designee) will explain to each subject the nature of the study, its purpose, the procedures involved, the expected duration, the potential risks and benefits involved and any discomfort it may entail. Each subject will be informed that participation in the study is voluntary, that he may withdraw from the study at any time, and that withdrawal of consent will not affect his subsequent medical treatment or relationship with the treating physician(s) or institution. The informed consent will be given by means of a standard written statement, written in non-technical language, which will be IRB approved. The subject should read and consider the statement before signing and dating it, and will be given a copy of the document. No subject will enter the study or have study-specific procedures done before his informed consent has been obtained.

In accordance with the Health Information Portability and Accountability Act (HIPAA), the written informed consent document (or a separate document to be given in conjunction with the consent document) will include a subject authorization to release medical information to the study sponsor and supporting agencies and/or allow these bodies, a regulatory authority, or Institutional Review Board access to subjects' medical information that includes all hospital records relevant to the study, including subjects' medical history.

All subjects considered for enrollment in the study must complete an IRB-approved informed consent prior to any study-specific procedures being performed.

To register a patient, the participating site must contact the Lead Center's Study Coordinator about a potential candidate prior to sending documents. Once acknowledgement is made, the following documents must be completed and faxed to [contact]) or e-mailed to the lead site:

- Signed patient consent form
- Eligibility checklist signed by the participating center PI or Co-I
- Copies of all source documentation verifying eligibility criteria

The Lead Site will review the documents to confirm eligibility. To complete the registration process, the Lead Center will:

- Assign a patient study number
- Randomize the patient onto a treatment arm
- Register the patient on the study with the Sidney Kimmel Comprehensive Cancer Center's Clinical Research Office.
- Fax or e-mail the unique patient study number and assigned study arm to the participating site.

Treatment must not commence until the patient has been registered with the Sidney Kimmel Comprehensive Cancer Center's Clinical Research Office and randomization has been completed by the coordinating center.

4.1.2 *Multicenter/Participating site registration*

Central registration for this study will take place at *SKCCC, Johns Hopkins University*.

Patient registration at each study site/institution will be conducted according to the institution's established policies. Before registration, patients will be asked to sign and date an Institutional Review Board (IRB)-approved consent form and a research authorization/HIPAA form. Patients must be registered with their local site/institution and also with the sponsor or Lead Site before beginning any treatment.

4.1.3 *Randomization*

After written informed consent has been obtained and eligibility has been established, the coordinating center will enter demographic and baseline characteristics in an interactive web response system (IWRS). The coordinating center will obtain the patient's randomization assignment from the IWRS and appropriately notify the study site. Randomization to one of the two treatment arms will occur in a 1:1 ratio. The randomization will be stratified by: Center, surgical margin status (R0 vs R1), PSA prior to salvage treatment (PSA ≥ 0.5 vs < 0.5 ng/mL), and pathologic Gleason score (7 vs 8-10). Minimization approach³⁷ will be applied to ensure balanced assignment to each treatment arm. The investigator and the patient will be blinded to treatment assignment.

5. **TREATMENT/INTERVENTION PLAN**

This study is a multi-center, double-blind, placebo controlled, randomized Phase II trial in patients with non-castrate PSA-recurrent prostate cancer after radical prostatectomy. Eligible patients will be randomized in a 1:1 ratio to one of two treatment arms: salvage radiation therapy (SRT) *plus* placebo (Arm A) or SRT *plus* enzalutamide (Arm B) (see schema below).

The following assessments and procedures will occur during the study. A schedule of assessments is provided in Table 1.

Table 1 Study Calendar

Procedures	Baseline		Treatment						Follow-up*		Off-Study
			Day 1‡ (Start of Drug)	Day 61‡ (Start of SRT)	Day 91##	Day 120‡ (End of SRT)	Day 151##	Day 180## (End of Drug)	Q3 mos ⁸ 24- months	Q3 mos ^{8,9} Till study ends	
Informed Consent	X	Randomization									
Demographics	X										
Medical History	X ¹										
Concurrent medications	X ¹			X	X	X	X	X	X		X
Height	X ¹										
Physical Exam, vitals, weight, ECOG	X ¹			X	X	X	X	X	X		X
Adverse event evaluation				X	X	X	X	X	X		X
Pill count/diary ¹²				X	X	X	X	X	X		X
CBC with diff ²	X ¹			X	X	X	X	X	X		X
Serum Chemistries ³	X ¹			X	X	X	X	X	X		X
Total serum testosterone	X ¹			X	X	X	X	X	X		X
PSA evaluation ⁴	X ¹			X	X	X	X	X	X ⁴	X	X
ECG ⁵	X ¹										
CT A/P (or MRI) ⁶	X ¹										X ⁶
Chest X-Ray											X ⁶
Radionuclide bone scan	X ¹										X ⁶
QoL questionnaires ⁷			X	X	X	X	X	X	X		X
Tumor Tissue banking ¹¹	X										
Decipher Test									X ¹⁴		
Treatments											
SRT ¹³				X	X	X					
Placebo PO daily (Arm A)				X	X	X	X	X			
Enzalutamide 160mg PO daily (Arm B)				X	X	X	X	X			

Abbreviations: CBC, complete blood count; CT, computerized tomography; EKG, electrocardiogram; MRI, magnetic resonance imaging; PSA, prostate-specific antigen; Mos, Month

1. All evaluations should be conducted within 30 days prior to registration/randomization. The exception to this is the radiologic evaluations and informed consent, which can be performed within 90 days prior to day 1.
2. CBC which includes WBC (with differential), platelets, Hgb, and Hct
3. Chemistries include albumin, alkaline phosphatase, total bilirubin, BUN, calcium, chloride, creatinine, glucose, sodium, potassium, total protein, SGOT [AST], and SGPT [ALT].
4. Those patients coming off study prior to PSA progression (i.e. for toxicity, etc.) should be evaluated for PSA levels every 3 months until PSA progression occurs.
5. ECGs may also be performed as clinically indicated throughout the study.
6. Radiologic evaluations (CT/MRI and bone scan) and chest x-ray (if applicable) should be conducted at PSA progression. Scans can also be obtained sooner as clinically indicated.
7. Quality-of-life (QoL) tools will include FACT-P, EORTC QLQ-C30/QLQ-PR25, and SHIM.
8. Patients should remain on study until PSA progression. This is defined as a PSA value ≥ 0.2 ng/mL above nadir that is confirmed by a second consecutive PSA value ≥ 8 weeks later which is higher (and ≥ 0.4 ng/mL). Patients should remain on study until the confirmatory PSA.
9. The total length of the study is 18 months for full enrollment and 24-months of follow-up for the last patient or 42 months. Patients who have 24-months of follow-up following treatment will continue to be followed for PSA determinations only and should remain on study until PSA progression or study end at month 42 whichever comes first.
10. To be conducted 2 months after the patient comes off study.
11. In patients who have consented, a tumor tissue block should be requested for banking, preferably from the prostatectomy specimen. If not available, a tissue block from the prostate biopsy should be submitted. In addition, a normal tissue block from the same patient (preferably from the prostatectomy) should be requested for banking. This only applies to the lead site (JHU).
12. Drug and diary review and dispensing may be done prior to or indicated day.
13. SRT to start 61 days (+/- 3 weeks) after Day 1. SRT will be delivered Monday-Friday
14. Decipher Test can be completed at any time before treatment ends on Day 180.

*Should occur within 7 days prior (Please note that this window does not apply to the study drug administration. The participant should take the study drug continuously for 180 days)

Should occur +/- 14 days (Please note that this window does not apply to the study drug administration. The participant should take the study drug continuously for 180 days)

*Follow-up visits may be performed +/- one month from the scheduled time of visit date. In the event that the participant chooses to undergo follow-up evaluation elsewhere or unexpectedly cannot adhere to the follow-up timeline, QoL assessments may be completed via mail or email and adverse event assessments may be completed by the study team via telephone.

Note that the study calendar is based on the ideal subject. The schedule should be followed as closely and realistically as possible, but may be modified due to problems such as scheduling delays, conflicts such as clinic closure or poor weather conditions, or other unforeseeable events.

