- Patients must be disease-free from prior malignancies for ≥ 3 years, with the exception of non-melanoma skin cancers and superficial urothelial cancers.
- Patients must have the ability to swallow the study drug whole as a tablet or capsule.
- Willingness to use adequate methods of contraception throughout study participation and for at least 3 months after completing therapy
- The patient was informed about the positive survival results of the RTOG 96-01 clinical trial, and has elected to forgo treatment with high-dose bicalutamide

Study centers Six sites in the United States, including the lead site (SKCCC, Johns Hopkins University)

Start date/Duration First patients are expected to be enrolled in March 2015. Accrual has been slower than originally estimated but we will end accrual March 2020 with additional 21 months of follow-up after the last patient has been entered.

Expected enrollment 96 patients

Rationale The primary hypothesis of this study is that outcomes for patients with biochemically recurrent prostate cancer following radical prostatectomy will be improved by the addition of enzalutamide

for 6-months compared to standard-of-care salvage radiation therapy to allow for further study in the definitive phase III setting. This study builds on the prior success of high-dose bicalutamide (for 24 months) when combined with salvage XRT, while using a newer more potent anti-androgen for a shorter duration of time (6 months) in an effort to minimize adverse effects.

[figure not shown]
Objectives Primary

The primary objective of the study is to evaluate the efficacy of the two treatment regimens in terms of freedom-from-PSA-progression (FFPP). FFPP is defined as the time from randomization to the date of PSA progression. In patients who achieve an undetectable PSA value (defined as ≤ 0.1 ng/mL), PSA progression is defined as a detectable PSA value (≥ 0.2 ng/mL) that is confirmed by a second consecutive PSA value obtained ≥ 8 weeks later which is higher (and ≥ 0.4 ng/mL). In patients who do not achieve an undetectable PSA, PSA progression is defined as a 0.2 ng/mL increase from nadir that is confirmed by a second consecutive PSA value obtained ≥ 8 weeks later which is higher.

Secondary

- Time to local recurrence within the radiation field (confirmed pathologically).

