5.2 Treatment Period

The following procedures are to be conducted each study visit on visit on Day 1, 61, 91, 120, 151 and 180 days while on study. Day 1, 61, 120 procedures should be done within seven days prior; day 91, 151 and 180 procedures should be done +/- 14 days (see Table 1):

- Review concurrent medications (see Appendix B for a listing of medications with the potential for drug interactions)
- Physical exam (vital signs, weight)
- ECOG performance status (Appendix A)
- Adverse events evaluation
- Review pill diary
- Laboratory tests (CBC w/diff, PSA, testosterone, comprehensive chemistry panel, including bilirubin, creatinine, SGOT[AST], SGPT[ALT])
- QoL questionnaires

The following procedures are to be conducted at each follow-up visit every 3 months ± 1 month up to 24 months (see Table 1). If participants are unable to return for follow-up, outside records may be obtained and assessments may be conducted via phone, email, or mail when possible:

- Review concurrent medications (see Appendix B for a listing of medications with the potential for drug interactions)
- Physical exam (vital signs, weight)
- ECOG performance status (Appendix A)
- Adverse events evaluation
- Laboratory tests (CBC w/diff, PSA, testosterone, comprehensive chemistry panel, including bilirubin, creatinine, SGOT[AST], SGPT[ALT])
- QoL questionnaires

The following procedure is to be conducted at each follow-up visit every 3 months ± 1 month past the first 24 months and up to 42 months (see Table 1):

- Laboratory test (PSA)

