6.1.2 Dosage Selected

6.1.2.1 Preparation, and Schedule of Administration

Enzalutamide or placebo: 160 mg PO once daily for 6 months (2 months prior to SRT, 2 months during SRT and 2 months following SRT). This consists of taking four 40-mg capsules all at one time. Enzalutamide or placebo is to be taken at the same time daily. Enzalutamide or placebo can be administered with/without food and needs no premedication. Treatment will be administered on an outpatient basis and agent dispensed at the time of pill diary review (see Table 1 – Study Calendar).

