7.4 Reporting Adverse Events

7.4.1 *Reporting serious adverse events*

Sponsor-Institution and Sponsor-Investigator shall be responsible for reporting any and all serious adverse events associated with the use of the Study Drug to the FDA via MedWatch (FDA Form 3500A), with a copy to Astellas via e-mail to [contact], or fax to [contact] and, when necessary, to the applicable IRB.

Life-threatening (grade 4 or 5) SAEs, events determined to be medically significant by the treating Investigator, and unknown reactions or unexpected events should be reported to the principal investigator, site IRB and the lead site/sponsor within 24 hours and be reported according to institutional and the following guidelines.

SAEs that are fatal and possibly protocol related and any treatment emergent seizure events should be reported by phone to the Protocol Chair immediately upon knowledge of the event.

The Lead Center's Study Coordinator should be contacted when reporting an SAE or death. If this person cannot be reached within 24 hours, the Protocol Chair (Lead Center's PI) should be contacted: [name], [contact].

The initial report for each SAE or death should include the following information:

- Protocol # and title
- Patient initials, study identification number, age
- Date the event occurred
- Description of the SAE
- Dose level and treatment month at the time the SAE occurred
- Description of the patient's condition
- Relationship of SAE to study drug/treatment (see Table 6)
- Indication whether the patient remains on study

Follow-up information including severity, causality, action taken, concomitant medications, and outcome should be communicated to the lead site/sponsor as soon as possible with an indication whether an amendment will need to be made to the protocol, the consent form, or both, as a result of this event.

7.4.2 *Reporting SAEs at multi-site/participating institutions*

A subject's AEs and SAEs will be recorded and reported from the signing of the ICF up to at least 30 days after completing salvage radiotherapy. The investigator must instruct the subject to report AEs and SAEs during this time period.

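### The registration step sends each patient's assigned arm to the participating site without naming a recipient; followed literally, it can reveal treatment to the blinded investigator

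*Combined protocol and SAP*

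**What the plan says.** Section 4.1.1 lists what the Lead Center does to complete a registration. It assigns a study number, randomizes the patient, registers him with the clinical research office, and then: "Fax or e-mail the unique patient study number and assigned study arm to the participating site". The addressee is the site as a whole.

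Section 4.1.3 describes the same event differently. The coordinating center obtains the "randomization assignment from the IWRS and appropriately notify the study site", and the paragraph ends: "The investigator and the patient will be blinded to treatment assignment". It does not say who at the site is notified, or what the notice contains.

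The synopsis, Section 5 and Section 10.1.1 all call the trial double-blind. Sections 5, 5.2.1 and 10.1.1 and the study calendar (Table 1) attach the letter A to placebo and B to enzalutamide.

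**The concern.** Anyone who knows the arm letter knows the treatment. A coordinator following Section 4.1.1 as written would send that letter, for every patient, to a site whose investigator is supposed not to know it.

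The safety data are most exposed. Section 7.3.3 makes the investigator responsible for judging each AE's relationship to enzalutamide. Section 10.3.1 reports AEs by attribution, and Section 10.1.2 characterizes both arms partly by relationship to therapy. Section 5.2.3 adds that, after the post-treatment visit, only new treatment-related events are recorded. For those later events the relatedness judgement would decide whether the event enters the data at all, not only how it is classified.

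**Working it through.** The point rests on reading the text, so the provisions are set side by side. The only arithmetic concerns how many patients a wording change can reach.

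1. **What is sent.** Section 4.1.1: study number and arm, by fax or e-mail, to the site. In the same exchange the site submits an eligibility form signed by its lead investigator or a co-investigator, so investigators are among the site's correspondents.
2. **What the label reveals.** Arm A is placebo and Arm B is enzalutamide, stated openly. The letter is not a code.
3. **Who is to be blinded.** Section 4.1.3 names two parties, the investigator and the patient.
4. **Whether anything limits the recipient.** Section 4.1.2 covers local and central registration only. Section 4.1.3 has the adverb *appropriately* and nothing more. Section 6.1.2.1 covers dosing and when drug is dispensed. Section 6.1.2.2 covers capsule contents, packaging, supplier and storage. None of them names an unblinded site role, a masked drug identifier used in place of the arm, or a person who holds the allocation. A placebo capsule does not protect the blind if the allocation itself is passed on.
5. **Where knowledge of the arm would enter.** It would enter causality attribution (7.3.3, reported under 10.3.1 and 10.1.2) and, if 5.2.3 governs, the recording of later AEs. The second route depends on which recording rule applies. Section 7.3.1 has all AEs documented whatever their suspected cause. Section 7.1.2 has all SAEs recorded while the patient is on study. Section 7.4.2 sets a further window tied to the end of radiotherapy. If 7.3.1 governs, only attribution is exposed.
6. **Where it would matter little.** FFPP is defined by PSA thresholds with a confirmatory value. The remaining judgement in 10.1.1 is the treating physician's view on whether a death was from prostate cancer, and that section expects such deaths to be very unlikely. Local recurrence requires pathological confirmation. Table 1, note 6, calls for scans at PSA progression in all patients, although earlier scans are allowed on clinical grounds. AE collection through the post-treatment visit does not depend on attribution (5.2.3).
7. **Scope of a wording change.** Inputs from Section 10.4.1: 80 patients enrolled by April 2019, a target of 96, about 10 patients per 6 months, and accrual ending March 2020.
   - Already enrolled: 80/96 = 83.3%.
   - Still to come under the target: 96 − 80 = 16, and 16/96 = 16.7%.
   - Projected at the stated rate over 12 months: 10 × (12/6) = 20. This exceeds 16, so the target sets the limit.

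**The case against.** The best reply is that the two sections can be read together. Section 4.1.3 is the dedicated randomization text. It says notification is to be appropriate and states the blind in the same paragraph. The site includes whoever dispenses drug, and a site told to keep its investigator blinded should not hand him the letter. Dosing and dose-reduction rules are written for enzalutamide or placebo alike, which fits a working blind. Details of dispensing and code-holding may also sit in a pharmacy or IWRS manual outside these documents.

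Much of this stands. It shows that the blind may have been kept in practice, and nothing in the documents shows otherwise. It does not remove the conflict: the only explicit instruction on content is to send the arm, and *appropriately* sets no limit on who reads it.

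A reader might also infer more than the documents support:

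- **That all site staff are meant to be blinded.** Section 4.1.3 covers only the investigator and the patient.
- **That the person who dispenses also assesses AEs.** Section 6.1.2.1 has the "agent dispensed at the time of pill diary review", and Section 5.2 lists "Review pill diary" alongside AE evaluation. This fixes timing, not who does it, and Table 1, note 12, allows dispensing before the visit day.
- **That the lead site's coordinator is a route for unblinding.** The synopsis counts "Six sites in the United States, including the lead site", the Lead Center's coordinator is the first contact for registration, and Section 7.4.1 says that the "Study Coordinator should be contacted when reporting an SAE or death". No text has this person randomizing patients, attributing causality or being blinded, so the overlap shows no breach.
- **That the share of follow-up under the relatedness rule measures the harm.** That share would be the same under perfect blinding, and the AE windows in 5.2.3, 5.5, 7.1.2, 7.3.1 and 7.4.2 differ. Those differences are a separate matter.

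**Conclusion.** The conflict is real and limited. As written, Section 4.1.1 can disclose treatment to the investigator whom Section 4.1.3 blinds, and no other text prevents it. The exposed results are AE attribution and, if the 5.2.3 rule governs, the recording of later AEs.

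Two stronger conclusions are not supported. The documents do not show that any investigator or patient learned the arm. They also give no ground for doubting the primary comparison on this account, because FFPP is largely protected.

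The size of any bias cannot be derived from the documents. What can be stated is reach: 80 of 96 patients (83%) were enrolled by April 2019 and at most 16 (17%) remained. Amended wording alone therefore leaves most of the trial unexamined. This assumes that enrolment stops at the target and that no unseen manual already restricts the notice. If one does, the check below would document it.

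**What to change.** - **Section 4.1.1.** State that the investigator and those who assess AEs receive only the patient study number and confirmation that randomization is complete. Send the assignment, or a masked drug identifier if one exists, only to the person who dispenses drug at the site and takes no part in assessment.
- **Section 4.1.3.** Use the same wording in place of the general reference to notifying the site.
- **Patients already randomized.** Check which roles received past notices, and report the result with the trial findings.
- **If disclosure is found.** Rest the between-arm safety comparison on the AE summaries already planned in 10.1.2 and 10.4.3, by frequency, body system and worst grade regardless of attribution. If 5.2.3 governed recording, say in the report that counts after the post-treatment visit still depend on the relatedness judgement.

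The cost is small: wording in two places, a change in who receives the notice, and a one-time check of the notices for the 80 or more patients already enrolled. No new patient data, sample size change or new analysis is needed. If the notices turn out to have been restricted all along, the check supports the double-blind claim.
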